2.2.2 KNOWN POTENTIAL BENEFITS

Exercise has been shown to reduce inflammation in other populations, but has not been studied much in people with SCI. Therefore, exercise may reduce inflammation in the SCI population, however this is not guaranteed. In addition, there will be no cost for individuals to participate in the exercise program, while enrolled in the study.

2.2.3 ASSESSMENT OF POTENTIAL RISKS AND BENEFITS

We believe the potential risks to the participants in this study are minimal and that the benefit of understanding whether exercise can reduce chronic inflammation and improve strength, cardiovascular health, and quality of life in patients with SCI outweighs the potential risks.

3 OBJECTIVES AND ENDPOINTS

OBJECTIVES	ENDPOINTS
Primary	
To examine the effect of a 12-week exercise program on inflammation in individuals with SCI.	Change in inflammatory biomarkers: CRP, IL-6, TNF- α
Secondary	
To examine the effect of a 12-week exercise program on strength and cardiovascular health in individuals with SCI.	Strength : 1-repetition maximum, Cardiovascular : 6-minute submaximal exercise test.
Tertiary	
To observe the impact of a 12-week exercise program on QOL in individuals with SCI.	SCI-QOL

4 STUDY DESIGN

4.1 OVERALL DESIGN

Study Design:

This study is an unblinded, randomized, 2-arm clinical trial.

Hypotheses:

Primary Hypothesis: We hypothesize that exercise will reduce inflammatory biomarkers.

Secondary Hypothesis: We hypothesize that exercise will improve strength and cardiovascular health.

Tertiary Hypothesis: We hypothesize that exercise will improve QOL.

Randomization:

At the consent visit, participants will be randomized into one of two treatment groups. Randomization is explained in **Section 6.3**.

Treatment Groups:

Group 1: 10 participants will begin the exercise program immediately (3x per week for 12 weeks = 36 total).

Group 2: After a 12-week delay, 10 participants will begin the exercise program (3x per week for 12 weeks = 36 total).

Study Intervention:

Exercise sessions will last approximately 1 hour and will be lead by exercise physiologists and therapists. Additional details are discussed in **Section 6.1**.

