1.2 SCHEMA

1.3 SCHEDULE OF ACTIVITIES

	Pre-screening	Consent	Pre-treatment 1	Pre-treatment 2	Study Intervention	Post-treatment 1	Post-treatment 2	Early Withdrawal Visit
Group 1: Immediate Start	Visit 0	Visit 1	Visit 2	N/A	Visit 3-38	Visit 39	Visit 40	
Group 2: Delayed Start				Visit 3	Visit 4-39	Visit 40	Visit 41	
Review Eligibility	X							
Informed Consent		X						
Randomization		X						
Demographics		X						
Medications		X	X	X	X	X	X	X
Blood Draw- in person			X	X		X	X	X
Strength & Cardiovascular Testing- in person			X	X		X	X	X
SCI-QOL- e-mail survey			X	X		X	X	X
Adverse Events (AE) Reporting					X	X	X	X
Treatment Adherence					X			

VISIT SCHEUDULE DESCRIPTION

All in-person visits will take place at: **HealthPartners Neuroscience Center, [name].**

1. Pre-screening Phone/Video Call (Groups 1 & 2)

- Duration: Approximately 30 minutes
- Research staff will:
 - Provide potential participants information about the study and ask whether they are interested in participating.
 - Determine whether they meet the inclusion/exclusion criteria for the study.
 - Ask participants for permission to communicate through e-mail for the study and assist them in setting up an account if they do not have one (e.g. send them study documents, QOL survey).
 - Schedule Consent Visit if the person is eligible for the study and e-mail the person the Informed Consent, Health Insurance Portability and Accountability Act (HIPAA), and HealthPartners non-discrimination forms.

2. Consent Phone Call (Groups 1 & 2)

- Duration: Approximately 1 hour via phone
- Research staff will:
 - Review the Informed Consent and HIPAA documents with potential participants.
 - Answer any questions of potential participants and ensure they understand the expectations of the study.
 - Ask participants to electronically sign the Informed Consent and HIPAA documents via REDCap and provide them electronic copies for their records.
 - Complete the Demographics short form in the relevant electronic case report forms (eCRFs) in Research Electronic Data Capture (REDCap), a secure web-based system.
 - Randomize the participant and schedule the Pre-treatment visit(s).

3. Pre-treatment Visit 1 (Groups 1 & 2)

- Duration: Approximately 1 hour in person
- Research staff will:
 - Complete the Medication review in REDCap.
 - Have the laboratory staff obtain a blood sample from the patient.

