5.4 SCREEN FAILURES

Pre-screening Phone Call:

All potential participants will undergo a pre-screening phone call to determine whether they meet the inclusion/exclusion criteria. Patients will be considered ineligible if they do not meet one or more of the inclusion/exclusion criteria during pre-screening. We will collect information on why participants are ineligible or decide not to move forward with the trial.

Pre-treatment Visit:

Screen failures are defined as participants who are considered eligible during the pre-screening phone call, but it was subsequently determined that they do not meet one or more of the inclusion/exclusion criteria at or after the Pre-treatment (baseline) visit. We will collect information on why participants screen fail or decide not to move forward with the trial.

Rescreening Patients:

Individuals who do not meet the criteria for participation in this trial (ineligible or screen failure) because of meeting one or more exclusion criteria that are likely to change over time may be rescreened up to one time. Examples include: patient no longer has sternal or spinal precautions; exercise program participation \leq 1 month from study enrollment; or participation in an interventional study \geq 3 months prior. Rescreened participants will be assigned a new participant number.

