6.1.2 ADMINISTRATION AND/OR DOSING

Exercise Program:

Twenty individuals with a SCI will participate in a 12-week strength and endurance adaptive exercise program. They will be enrolled into our already existing NeuroWell program, which is an exercise program geared toward individuals with neurological disorders or injuries run by the Regions Hospital Rehabilitation department at the HealthPartners Neuroscience Center. Prior to participating in the exercise program, the prospective participant will provide a medical clearance by their physician. Certified Clinical Exercise Physiologists will supervise the program. Therapists will also assist with the program as needed. The exercise programming will be designed by the exercise physiologists and adapted to individuals' abilities. Exercise prescriptions will be designed based on established guidelines, level and completeness of injury, individual functional ability, individual goals, and baseline exercise assessments.

The American College of Sports Medicine recommends that those with an SCI participate in 2-3 exercise sessions per week consisting of moderate intensity (40-59% Heart Rate Reserve) aerobic exercise, light to moderate intensity (20 RM to 10 RM) resistance training, and daily flexibility training. Therefore, participants will exercise 3 times a week during the 12-week program, following these guidelines. Each session will consist of 20-30 minutes of endurance exercise, 20 minutes of resistance training, and 10 minutes of flexibility, core exercises, and seated balance training. Types of exercise and equipment utilized are described in Table 1. The program will allow individuals who have suffered a SCI to access an exercise program that is adaptive to their current function and tailored to their individual fitness goals.

Table 1. Exercise Session Components

Endurance/Aerobic	Strength/Resistance	Flexibility, Core, Balance
FES Cycle (Restorative Therapies, Inc) (Figure 1a)	IncludeStrength (IncludeHealth) (Figure 1d)	Passive
Upper Body Ergometer (SCIFIT) (Figure 1b)	Resistance Machines (leg press, chest press, lat pulldown, rowing machine, CanDo Rickshaw)	Active
Wheelchair Ergometer (Wheelers' Paramill) (Figure 1c)	Resistance Bands (Theraband)	Active-Assisted
	Ankle/wrist cuff weights	Functional Activities (e.g. mat exercises)

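### Randomisation on the consent call comes before every baseline measurement, so effort-dependent baselines are taken with allocation known and later screen failures are already randomised

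*Combined protocol and SAP*

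**What the plan says.** On timing, section 4.1 reads: "At the consent visit, participants will be randomized into one of two treatment groups". The schedule in section 1.3 marks randomisation in the consent column (Visit 1) and describes that visit as "Duration: Approximately 1 hour via phone". On the same call, staff book the pre-treatment visits: one for Group 1, two for Group 2.

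On eligibility, at the pre-screening phone or video call (Visit 0) staff are to "Determine whether they meet the inclusion/exclusion criteria for the study". No later column of the schedule is marked for eligibility review. Section 5.4 nevertheless defines screen failures as people who passed the phone check but who "do not meet one or more of the inclusion/exclusion criteria at or after the Pre-treatment (baseline) visit". On clearance, section 6.1.2 says: "Prior to participating in the exercise program, the prospective participant will provide a medical clearance by their physician".

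On blinding, sections 4.2 and 6.3 say that neither staff nor participants are blinded, because the start date reveals the group.

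On analysis, section 9.4.2 uses ANCOVA on change with the baseline value as covariate. Sections 9.4.3 and 9.4.4 apply the same structure to HR, RPE, maximal weight and SCI-QOL. Section 9.3 commits all analyses to intention to treat, section 9.4.1 drops participants with incomplete assessments, and section 7.2 allows replacement of randomised people who never receive the intervention.

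**The concern.** The lack of blinding is justified by the delayed start, which cannot be hidden once participants are waiting or exercising. That argument covers follow-up. It does not cover baseline, which could be taken before anyone knows the arm.

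Two things are at stake. First, a 1-repetition maximum, a perceived-exertion rating and a quality-of-life questionnaire can all respond to knowing whether one starts now or in 12 weeks, and staff encouragement can respond too. An artefact at baseline that is not repeated at follow-up passes into the estimated effect. Second, when final eligibility is judged after allocation by people who know the arm, exclusion and replacement can differ between arms. With about ten people per arm, a few such decisions matter.

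**Working it through.** **1. Order of events (section 1.3)**

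| Visit | Mode | Content |
|---|---|---|
| 0, pre-screening | phone or video | eligibility review |
| 1, consent | phone | consent, demographics, randomisation |
| 2, Pre-treatment 1 | in person; survey by e-mail | blood draw, strength and cardiovascular tests; SCI-QOL within 3 days |

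Every baseline value used as a covariate comes from Visit 2 or up to 3 days after it, so after allocation. Because the number of visits booked at Visit 1 differs by group, allocation is known to both sides by the end of that call.

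**2. Eligibility**

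Section 5.1 requires a physical finding (active shoulder flexion of at least 90°), and section 5.2 includes an investigator's judgement on spasms. Before randomisation these can be assessed only by phone or video. Since Visit 2 follows randomisation, every screen failure in the section 5.4 sense has already been randomised. Section 5.4 also permits one rescreen under a new participant number, without saying what becomes of an allocation already made. No section says whether screen failures or replaced people stay in the intention-to-treat set.

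**3. Size of a baseline artefact**

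Let knowledge of allocation shift one arm's measured baseline by s (in SD), leaving follow-up unchanged. Let b be the ANCOVA slope of follow-up on baseline. The adjusted difference is

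(difference in follow-up means) − b × (difference in baseline means),

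so it moves by b × s in absolute value. The group coefficient is the same whether change or follow-up is the outcome. The raw difference in mean change moves by the full s.

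Neither s nor b is in the documents. Both ranges are assumptions.

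| s (SD) | b = 0.5 | b = 0.7 |
|---|---|---|
| 0.1 | 0.05 | 0.07 |
| 0.2 | 0.10 | 0.14 |
| 0.3 | 0.15 | 0.21 |

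The standard error of an unadjusted difference with 10 per arm is √(2/10) = 0.45 SD, and 0.21/0.45 = 0.47. If baseline and follow-up have equal variance, b equals their correlation and the adjusted standard error at b = 0.7 is about 0.45 × √(1 − 0.49) = 0.32 SD, giving 0.21/0.32 = 0.66. The direction is unknown: low baseline effort in Group 1 would flatter the program, and low effort in Group 2 would count against it.

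**4. Loss before the intervention**

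Sections 4.1, 6.1.2 and 9.2 work with 20 participants; the synopsis and section 5.5 have 25. Section 10.4 records the increase as replacement of people who withdrew before the intervention. The difference is (25 − 20)/25 = 20% of those to be randomised.

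**5. The plan's own power figure**

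A two-sided two-sample t-test with 10 per arm at 5% has 78.5% power at 1.3 SD and 80.0% at 1.325 SD, which rounds to 1.3. The stated 80% therefore reproduces, and moving randomisation leaves it unchanged.

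**The case against.** The strongest reply is that the effect is modest and falls outside the primary endpoint. CRP, IL-6 and TNF-α are laboratory assays and do not depend on effort. The outcomes most exposed are secondary or tertiary, the shift is hypothetical, and even 0.21 SD is below half the unadjusted standard error. This largely stands. It limits the point without answering it, because the exposure is avoidable and adds error that a larger sample would not remove. Known allocation could also affect who attends the baseline blood draw.

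Several stronger readings are tempting, and the documents do not support them:

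- That ineligible people are being randomised. Criteria are checked at Visit 0, so the plan shows only that they can be.
- That physician clearance follows randomisation. Section 6.1.2 places it only before exercise. Randomising first is permitted but not stated.
- That 20% are lost because of the timing. Section 10.4 does not call the withdrawals eligibility failures or date them. Some could fall in Group 2's 12-week wait, which later randomisation would not prevent. A Group 2 participant who leaves after Pre-treatment Visit 2 still has both primary measurements.
- That intention to treat is abandoned. Nothing says screen failures are removed from that set. The gap is silence on how they are counted.

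A practical objection also stands in part: section 10.4 shows that blood draws and withdrawals have already occurred, so an amendment can reach only later enrolees.

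**Conclusion.** The point holds for the sequence. Sections 1.3 and 4.1 agree that randomisation precedes every baseline measurement, and nothing elsewhere remedies it. Effort-dependent and self-reported baselines are taken with the arm known. Under assumed shifts of 0.1 to 0.3 SD and slopes of 0.5 to 0.7, this would move the adjusted contrast by about 0.05 to 0.21 SD, in a direction that cannot be predicted. The estimate assumes that the artefact affects one arm's baseline only and does not recur at follow-up.

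For the primary biomarkers the baseline problem is minor. What matters there is that post-randomisation screen failures and replacements have no analysis rule. The rise to 25 shows that participants were lost before the intervention, and says nothing about why. The change should be made where enrolment still allows it. The analysis-set statement is needed in any case.

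**What to change.** For participants not yet randomised, amend sections 1.3, 4.1 and 6.3 so that randomisation follows Pre-treatment Visit 1. It should happen once the blood draw, strength and cardiovascular tests, eligibility confirmation and physician clearance are complete, and SCI-QOL has been returned or its 3-day window has closed. Allocation is then given by phone. In section 5.4, count people who fail before that moment as screen failures who were never randomised.

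In section 9.3, state that everyone already randomised stays in the intention-to-treat set, including those later found ineligible and those replaced. Report both groups by arm, with reasons.

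The cost is one amendment and a few days before participants learn their start date. No visit, staff or participant is added, since both groups already attend Pre-treatment Visit 1. Clearance should be requested early so that it does not lengthen the gap between baseline and allocation; the documents do not say how long it takes. If enrolment is under way, the sample will contain two randomisation timings, and the report should give the number under each.

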4.2 SCIENTIFIC RATIONALE FOR STUDY DESIGN

Justification for an unblinded study: Because it will be clear to both study personnel and participants who will have a delayed start and who will start immediately, neither will be blinded in this study. This will be reported as a limitation of the study.

Justification for an uncontrolled study with no control group: N/A

4.3 JUSTIFICATION FOR INTERVENTION

Exercise is well known to have positive health effects, such as reducing inflammation and improving fitness and cardiometabolic health. For this study, we anticipate that a 3-month adaptive exercise program will reduce chronic inflammation and improve overall health in individuals with SCI.

4.4 END-OF-STUDY DEFINITION

A participant is considered to have completed the study if he or she has completed study treatment visits and assessments. The end of the study is defined as completion of the last post-treatment visit for each group.

5 STUDY POPULATION

5.1 INCLUSION CRITERIA

In order to be eligible to participate in this study, an individual must meet all of the following criteria:

- Ability to provide and provision of signed and dated informed consent form
- Age 18-70
- Diagnosis of SCI and post injury \geq 6 months
- Able to achieve adequate active range of motion at the elbow and wrist (flexion/extension) and able to achieve at least 90° active shoulder flexion, in order to complete study activities

5.2 EXCLUSION CRITERIA

An individual who meets any of the following criteria will be excluded from participation in this study:

- Non-English speaking
- Exercise program participation \leq 1 month from study enrollment or any other exercise participation during the duration of the study
- Patients with significant cognitive impairment of any etiology that prevents them from being able to participate
- Patients that were given sternal or spinal precautions that would prevent excessive twisting, bending, overhead reaching and lifting over 10 pounds
- Patients with a history heart failure, chronic lung disease, angina or any other condition that causes unreasonable shortness of breath on exertion
- Has been diagnosed with autonomic dysreflexia that is severe, unstable, and uncontrolled
- Requires ventilator support
- Spasms that limit the ability of the subjects to participate in the study training as determined by the Investigator
- Pregnant, planning to become pregnant
- Any other medical conditions that could affect their ability to participate in the exercise program (as determined by study investigators)
- Active participation or past participation \leq 3 months in any other interventional study.
- Unwilling to participate in all study related activities

5.3 LIFESTYLE CONSIDERATIONS

N/A

5.4 SCREEN FAILURES

Pre-screening Phone Call:

All potential participants will undergo a pre-screening phone call to determine whether they meet the inclusion/exclusion criteria. Patients will be considered ineligible if they do not meet one or more of the inclusion/exclusion criteria during pre-screening. We will collect information on why participants are ineligible or decide not to move forward with the trial.

Pre-treatment Visit:

Screen failures are defined as participants who are considered eligible during the pre-screening phone call, but it was subsequently determined that they do not meet one or more of the inclusion/exclusion criteria at or after the Pre-treatment (baseline) visit. We will collect information on why participants screen fail or decide not to move forward with the trial.

Rescreening Patients:

Individuals who do not meet the criteria for participation in this trial (ineligible or screen failure) because of meeting one or more exclusion criteria that are likely to change over time may be rescreened up to one time. Examples include: patient no longer has sternal or spinal precautions; exercise program participation \leq 1 month from study enrollment; or participation in an interventional study \geq 3 months prior. Rescreened participants will be assigned a new participant number.

5.5 STRATEGIES FOR RECRUITMENT AND RETENTION

Recruitment: Individuals with SCI will be recruited by physician and therapist referrals from HealthPartners' clinics. We will also advertise our research study by distributing flyers to HealthPartners' physicians and throughout HealthPartners' and Park Nicollet clinics. Recruitment flyers will also be provided to our community partners, for example, the Minnesota Spinal Cord Injury Association and the Get Up Stand Up to Cure Paralysis Foundation. If we encounter difficulties with recruitment, we plan to submit an amendment to the IRB to contact HealthPartners patients and members and invite them to participate. To reach our target enrollment, we anticipate that we will need to screen 60 people, of those 25 individuals will sign the informed consent and will be randomized to treatment groups.

Remuneration: Participants will be provided gift cards totaling \$20 per person for completing certain time points of the research study. Group 1: Will receive a \$20 gift card at each of the pre- and post-treatment visits (3 visits \times \$20 = \$60 total). Group 2: Will receive a \$20 gift card at each of the pre- and post-treatment visits (4 visits \times \$20 = \$80 total).

6 STUDY INTERVENTION(S) OR EXPERIMENTAL MANIPULATION(S)

6.1 STUDY INTERVENTION(S) OR EXPERIMENTAL MANIPULATION(S) ADMINISTRATION

6.1.1 STUDY INTERVENTION OR EXPERIMENTAL MANIPULATION DESCRIPTION

The study intervention for both groups is an adaptive exercise program. The exercise program is described next in more detail.

6.1.2 ADMINISTRATION AND/OR DOSING

Exercise Program:

Twenty individuals with a SCI will participate in a 12-week strength and endurance adaptive exercise program. They will be enrolled into our already existing NeuroWell program, which is an exercise program geared toward individuals with neurological disorders or injuries run by the Regions Hospital Rehabilitation department at the HealthPartners Neuroscience Center. Prior to participating in the exercise program, the prospective participant will provide a medical clearance by their physician. Certified Clinical Exercise Physiologists will supervise the program. Therapists will also assist with the program as needed. The exercise programming will be designed by the exercise physiologists and adapted to individuals' abilities. Exercise prescriptions will be designed based on established guidelines, level and completeness of injury, individual functional ability, individual goals, and baseline exercise assessments.

The American College of Sports Medicine recommends that those with an SCI participate in 2-3 exercise sessions per week consisting of moderate intensity (40-59% Heart Rate Reserve) aerobic exercise, light to moderate intensity (20 RM to 10 RM) resistance training, and daily flexibility training. Therefore, participants will exercise 3 times a week during the 12-week program, following these guidelines. Each session will consist of 20-30 minutes of endurance exercise, 20 minutes of resistance training, and 10 minutes of flexibility, core exercises, and seated balance training. Types of exercise and equipment utilized are described in Table 1. The program will allow individuals who have suffered a SCI to access an exercise program that is adaptive to their current function and tailored to their individual fitness goals.

Table 1. Exercise Session Components

Endurance/Aerobic	Strength/Resistance	Flexibility, Core, Balance
FES Cycle (Restorative Therapies, Inc) (Figure 1a)	IncludeStrength (IncludeHealth) (Figure 1d)	Passive
Upper Body Ergometer (SCIFIT) (Figure 1b)	Resistance Machines (leg press, chest press, lat pulldown, rowing machine, CanDo Rickshaw)	Active
Wheelchair Ergometer (Wheelers' Paramill) (Figure 1c)	Resistance Bands (Theraband)	Active-Assisted
	Ankle/wrist cuff weights	Functional Activities (e.g. mat exercises)

Improvements in fitness and health outcomes will be optimized through the utilization of adaptive equipment and expert exercise programming. Novel, adaptive equipment and technology is integrated into the exercise program to accommodate varying levels of abilities. The RT300 Functional Electrical Stimulation (FES) Leg | Core cycle (Figure 1a; Restorative Therapies, Inc) transmits electrical pulses through surface electrodes, which allows individuals with little or no lower limb voluntary movement to pedal. The Pro1 upper body ergometer (Figure 1b; SCIFIT) is a versatile arm exerciser that includes a removable seat and wheelchair platform for easy wheelchair access. The wheelchair ergometer (Figure 1c; Wheelers' Paramill) is a treadmill designed to fit all manual wheelchairs and allows for backward and forward motion. The IncludeStrength (Figure 1d; IncludeHealth, Inc) machine includes movable seating for wheelchair access, the ability to secure a wheelchair, and dexterity-free handles. Finally, the exercise program will have access to specialty equipment to offer further adaptive support such as gripping aids (Active Hands) and leg stabilizers (NuStep, Inc).

Figure 1. Adaptive Equipment

Biomarker Quantification (Aim 1): The primary outcome for Aim 1 will be change in inflammatory biomarkers: CRP, IL-6, TNF- α , as these were the primary biomarkers shown to be higher in individuals with SCI compared to healthy individuals in previous studies. Patients in Group 1 will undergo 3 blood draws and patients in Group 2 will undergo 4 blood draws. Patients will give approximately 2.5 teaspoons of blood for each blood draw. Blood samples will be collected by the HealthPartners Neuroscience Center laboratory staff. CRP will be analyzed through Regions Hospital Central Laboratory. IL-6 and TNF- α will be analyzed using the MAGPIX® by Millipore Sigma™, a multiplex ELISA, allowing the quantification of multiple analytes from a single sample by combining magnetic and fluorescent technology. After collection, blood will be allowed to clot for at least 30 minutes before centrifuging for 10 minutes at 1000xg. Serum will be removed, aliquoted and stored in sterile cryo-preservation tubes in -80°C freezers onsite in a secured location with temperature tracking until time of analysis. At the time of analysis samples will be thawed and diluted 1:2 in Assay Buffer provided by a custom Milliplex® kit: HCTYA-60K-03 (IL6, TNFa, IL1RA). The beads provided by the kit will also be added and the plate will be incubated on a plate shaker following the kit protocol. After incubation the plate will be placed on a magnet and washed, then incubated with a secondary antibody provided by the kit. Once the secondary incubation is completed the plate will be again placed on a magnet and washed before being run by the MAGPIX®. Data quantification will be acquired using the xPonent® software provided by Millipore Sigma™.

Strength and Cardiovascular Health (Aim 2): Participants will undergo a strength and cardiovascular test during the pre-treatment and first post-treatment visits. The strength test will consist of a 1-repetition maximum chest press test. This test quantifies the amount of weight that participants can possibly lift during the one repetition. The cardiovascular test will consist of a 6-minute submaximal exercise test using an arm ergometer following previously published methods.¹⁴ Heart rate (HR) and blood pressure will be

measured before and after the test. Rate of perceived exertion (RPE), a measure of physical activity intensity, will be measured after the test.

Spinal Cord Injury-Quality of Life (Aim 3): Participants will be asked to complete the Spinal Cord Injury-Quality of Life (SCI-QOL) short forms at the pre-treatment and post-treatment visits. The SCI-QOL includes the following domains: basic mobility, fine motor, manual/power wheelchair, self-care, ability to participate in social roles and activities, anxiety, bladder complications, bladder/bowel management difficulties, depression, grief/loss, independence, pain behavior, pain interference, positive affect and well-being, pressure ulcer, resilience, satisfaction with social roles and activities, self-esteem, stigma, and trauma. The SCI-QOL has strong reliability and validity.¹⁵

